6.2. Preparation/Handling/Storage/Accountability

All study drug should be stored in the refrigerator at controlled temperatures ranging from 36°F to 46°F (2°C to 8°C). Site should keep the study drug cartons until ready to be used, protect them from direct heat and light, and avoid shaking the safety injectors. Study drug can be left out at room temperature up to 8 hours.

Study drug administration should be captured in the source documents and eCRF. JNJ-64565111 will be manufactured and provided under the responsibility of the sponsor.

The investigator is responsible for ensuring that all study drug received at the site is inventoried and accounted for throughout the study. The dispensing of study drug to the subject, and the return of study drug from the subject (if applicable), must be documented on the drug accountability form and/or interactive web response system (IWRS) drug accountability web portal. Details on drug accountability will be outlined in the IWRS site user manual. All study drug will be stored and disposed of according to the sponsor's instructions.

Subjects should be instructed to return the following at the drug return visits:

- unused safety injectors
- empty study drug cartons
- study drug diary

Study drug must be handled in strict accordance with the protocol and the study drug label, and must be stored at the study site in a limited-access area or in a locked cabinet under appropriate environmental conditions. Unused study drug, and study drug returned by the subject, must be available for verification by the sponsor's study-site monitor during on-site monitoring visits. The return to the sponsor of unused study drug for destruction, will be documented on the drug return form and/or IWRS drug accountability web portal. When the study site is an authorized destruction unit and study drug supplies are destroyed on-site, this must also be documented on the drug return form and/or IWRS drug accountability web portal.

Potentially hazardous materials such as used safety injectors containing residual liquids should be disposed of immediately in a safe manner and therefore will not be retained for drug accountability purposes.

Study drug should be dispensed under the supervision of the investigator or a qualified member of the study-site personnel, or by a hospital/clinic pharmacist. Study drug will be supplied only to subjects participating in the study. Returned of unused study drug must not be dispensed again, even to the same subject. Study drug may not be relabeled or reassigned for use by other subjects. The investigator agrees neither to dispense the study drug from, nor store it at, any site other than the study sites agreed upon with the sponsor.

6.3. Measures to Minimize Bias: Randomization and Blinding

Randomization and Blinding Procedures

On Day 1, subjects will be randomly assigned to 1 of 4 treatment groups based on a computer-generated randomization schedule prepared before the study by or under the supervision of the sponsor. The randomization will use randomly permuted blocks.

At baseline (Day 1), the treatment code, which is linked to the randomization schedule, will be assigned after logging on to the IWRS designated by the sponsor. The requestor must use his or her own user identification and personal identification number when contacting the IWRS, and will then give the relevant subject details to uniquely identify the subject. Based on this information, the IWRS will assign a unique treatment code, which will dictate the treatment assignment and matching study drug kit for the subject. As subjects are randomly assigned to treatment, the IWRS will assign a study drug kit to be dispensed at that visit. New study drug kits will be assigned each time the IWRS is accessed for dispensing additional study drug.

Blinding

The investigator will not be provided with randomization codes. The codes will be maintained within the IWRS, which has the functionality to allow the investigator to break the blind for an individual subject.

Data that may potentially unblind the study drug assignment (ie, study drug serum concentrations, anti-JNJ-64565111 antibodies, study drug preparation/accountability data, study drug allocation, FPG, HbA_{1c}, serum β -hydroxybutyrate, and urine ketones) will be handled with special care to ensure that the integrity of the blind is maintained and the potential for bias is minimized. This can include making special provisions, such as segregating the data in question from view by the investigators, clinical team, or others as appropriate until the time of database lock and unblinding.

Under normal circumstances, the blind should not be broken until all subjects have completed the study and the database is finalized. The investigator may in an emergency determine the identity of the study drug by contacting the IWRS. While the responsibility to break the study drug code in emergency situations resides solely with the investigator, it is recommended that the investigator contact the sponsor or its designee if possible to discuss the particular situation, before breaking the blind. In the event the blind is broken, the sponsor must be informed as soon as possible. The date and reason for the unblinding must be documented in the appropriate section of the eCRF and in the source document. The documentation received from the IWRS indicating the code break must be retained with the subject's source documents in a secure manner so as not to unblind the treatment assignment to the study site or sponsor personnel. The investigator is also advised not to reveal the study treatment assignment to the study site (except as necessary for the clinical management of the subject) or sponsor personnel.

In general, treatment codes will be disclosed fully only after the study is completed and the clinical database is closed.

6.4. Study Drug Compliance

The investigator or designated study-site personnel will maintain a log of all study drug dispensed and returned. Drug supplies for each subject will be inventoried and accounted for throughout the study. Subjects who are poorly compliant with blinded study drug (based on unused safety injector(s), used empty study drug cartons, and/or study drug diary) should receive counseling on the importance of dosing compliance.

During the course of the study, the investigator or designated study-site personnel will be responsible for providing additional instructions to re-educate any subject who is not compliant with taking the study drug.

6.5. Prestudy and Concomitant Therapy

Prestudy therapy includes any therapy used before the first dose of treatment phase study drug. Concomitant therapy is any therapy used after the first dose of treatment phase study drug that is administered on Day 1.

Prestudy therapies administered up to 30 days before first dose of double-blind treatment phase study drug must be recorded.

All therapies (prescription or over-the-counter medications, including vaccines, vitamins, herbal supplements; non-pharmacologic therapies such as electrical stimulation, acupuncture, special diets, exercise regimens) different from the study drug must be recorded in the eCRF.

Prohibited Therapies

1. Prescription weight-management drugs (including but not limited to orlistat, topiramate and/or phentermine, lorcaserin, naltrexone and/or bupropion), or over-the-counter weight-loss medications or therapies
2. Oral, intravenous, or intramuscular corticosteroids for longer than 2 consecutive weeks in duration
Note: Inhaled, intranasal, intra-articular, or topical corticosteroids, or corticosteroids in therapeutic replacement doses are allowed
3. Previous (ie, within 12 weeks from screening visit) or current use of a highly active anti-retroviral therapy
4. GLP-1 agonists and any insulin except basal insulin that serve as rescue AHA use
Note: if a subject temporarily requires insulin treatment due to a transient condition (eg, due to hospitalization, surgery, or other acute illness) for ≤ 7 days, they may remain in the study
5. Antipsychotic drugs
6. Anticonvulsants
7. Tricyclic antidepressants, lithium, levodopa, and dopamine receptor agonists
8. Any other investigational agents during the study

The sponsor must be notified in advance (or as soon as possible thereafter) of any instances in which prohibited therapies are administered.

6.6. Glycemic Rescue Medication

During the 12-week treatment phase, glycemic rescue therapy will be implemented in subjects with FPG values (repeated and confirmed within 7 days) meeting the prespecified criteria provided in Table 3 below. Subjects should be counseled to contact the site if their fasting SMBG consistently (ie, ≥ 3 days within a week) exceeds 200 mg/dL, and an FPG measurement to determine eligibility for glycemic rescue therapy should be obtained. Subjects should have reinforcement of diet and exercise recommendations before obtaining the repeat FPG value. At the investigator's discretion, based upon recent fasting SMBG values that are consistent with the initial FPG result meeting glycemic rescue criteria, this single FPG (ie, without a repeat FPG value) may be used to demonstrate eligibility for glycemic rescue therapy.

Table 3: Glycemic Rescue Criteria

Time point	Value
After Day 1 through Week 6	FPG >270 mg/dL (>15 mmol/L)
After Week 6 through Week 12	FPG >240 mg/dL (>13.3 mmol/L)

Rescue therapy may include increasing the dose of a current AHA or the initiation of a new AHA. Investigators will manage rescue therapy, including the selection of the specific AHA, its clinically appropriate initial dose and titration regimen (if applicable), the need to switch from one AHA rescue medication to another (eg, poor glycemic response to prior rescue medication), and be consistent with the labeled use within the country of the study site. Metformin, sulphonylureas, TZDs, SGLT-2 inhibitors, DPP-4 inhibitors, and insulin (basal only) are allowed as rescue medication. Both GLP-1 agonists and short-acting or intermediate insulins are not allowed as rescue medications.

Subjects on glycemic rescue therapy for at least 2 weeks at the maximum dose considered appropriate by the investigator, with FPG >180 mg/dL (10.0 mmol/L), must be discontinued from the study drug treatment (see Section 7, Discontinuation from Study Drug and Discontinuation from Study).

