Counseling should be done by dietitians/nutritionists on Day 1 to provide assessment and recommendation on a reduced-calorie diet and exercise regimen. In addition, subjects will be counseled on maintaining proper hydration throughout the study especially in circumstances of potential dehydration (eg, nausea and vomiting). At subsequent visits (Week 2 and Week 6), counseling and reinforcement of the recommended diet/exercise and hydration regimens will be conducted by a trained counselor. In addition, beginning at Week -2 visit, subjects will be counseled to comply and perform fasting self-monitored blood glucose (SMBG) testing at least 2 times per week. At each treatment visit, the investigator or qualified, assigned designee will review the subject's diaries, concomitant medications and the adverse events (AEs) that started or changed since the last visit.

Study Drugs Administered

Open-label AHA Background Therapy

Subjects on oral AHA will be required to have been on a stable treatment regimen (ie. same agent and same dose) for at least 12 weeks prior to screening and to remain on such regimen throughout the remainder of the study.

Antihyperglycemic agents allowed at screening and as glycemic rescue medication during study are: metformin, sulphonylureas, dipeptidyl peptidase-4 (DPP-4) inhibitors, sodium-glucose cotransporter 2 (SGLT-2) inhibitors, and thiazolidinediones (TZDs).

Basal insulin is not allowed at screening but can be used as a glycemic rescue medication.

On days of protocol-specified study visits, subjects are to withhold their morning dose of subjects' oral AHA until after the completion of all study visit procedures.

JNJ-64565111/Placebo During Run-in Period

At the Week -2 visit, subjects will be instructed on the use of prefilled safety injectors to perform subcutaneous (SC) self-injections, and will be asked to perform a self-injection in the presence of the study-site staff. Only subjects who express willingness and demonstrate the ability to administer once weekly SC injections are eligible to participate in the study. To assess compliance with the dosing regimen, eligible subjects will be dispensed prefilled safety injectors containing 0.5 mL open-label placebo and instructed to perform self-injections once weekly at home during the run-in phase, as well as keep a study drug diary of their injection schedule.

Double-blind JNJ-64565111 or Matching Placebo During Double-Blind Treatment Period

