Subjects are to record the date and time of study drug administration on the study drug diary, and should mark a calendar to **remind** them of when to take the next weekly dose. Subjects will be instructed to record the date and time of each self-injection throughout the run-in and treatment phase which allows an assessment of treatment compliance and the relationship of PK measurements and safety assessments to the time of study-drug dosing. The information will be entered into electronic case report forms (eCRFs) by the site personnel.

Subjects should be instructed not to take 2 doses within 3 days (72 hours) of each other. If a subject misses taking the next dose of study drug on their regularly scheduled study drug day, the missed dose should be taken as soon as possible, if there are at least 3 days (72 hours) until their next regularly scheduled study drug day. If there are less than 3 days remaining, the subject should skip the missed dose and take the next dose on their regularly scheduled study drug day.

Glycemic Rescue Medication

During the 12-week treatment phase, glycemic rescue therapy will be implemented in subjects with FPG values (repeated and confirmed within 7 days) meeting the prespecified criteria. Subjects should be counseled to contact the site if their fasting SMBG consistently (ie, ≥ 3 days within a week) exceeds 200 mg/dL, and an FPG measurement to determine eligibility for glycemic rescue therapy should be obtained. Subjects should have reinforcement of diet and exercise recommendations before obtaining the repeat FPG value. At the investigator's discretion, based upon recent fasting SMBG values that are consistent with the initial FPG result meeting glycemic rescue criteria, this single FPG (ie, without a repeat FPG value) may be used to demonstrate eligibility for glycemic rescue therapy.

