1.3. Schedule of Activities (SoA)

Protocol Activity	Pre-treatment			Treatment Phase								Post-treatment
	Screening	Run-In		Day 1 (Randomization)	Day 4	Wk 2	Wk 4 (RC) ^a	Wk 6	Wk 10 (RC) ^a	Wk 11	Wk 12/ EOT ^b	
Wk -3	Wk -2	Wk-1										
Screening/Administrative												
Informed consent ^d	X											
Inclusion/exclusion criteria	X	X		X								
Medical history & demographics	X											
Prior therapy reporting and review ^e	X	X		X								
IWRS log-in	X	X		X		X		X			X	
Randomization				X								
Study Drug Administration												
Show and/or describe injection device		X										
Dispense run-in medication		X										
Dispense double-blind medication				X		X		X				
Injection at study site ^f		X		X								
Dispense study drug diary		X		X		X		X				
Review study drug diary				X		X		X			X	
Run-in compliance assessment				X								
Drug return and accountability				X		X		X			X	
Survey on self-administration of study drug ^g								X				
Clinical Procedures												
Physical examination ^h	X										X	
Vital signs (PR and BP, in triplicate) ⁱ	X			X		X		X			X	
Weight ^j	X			X		X		X			X	
Height	X											
Waist circumference ^j				X							X	
12-lead ECG (local)		X										
Laboratory Assessments ^k												
Fasting fingerstick glucose ^{l,m}				X								
Glycated hemoglobin (HbA _{1c})	X			X		X		X			X	
Fasting plasma glucose (FPG) ^l	X			X		X		X			X	
Fasting C-peptide ^l	X			X							X	
Fasting insulin ^l				X							X	
Fasting lipid profile ^l	X			X							X	
Serum chemistry	X			X		X		X			X	

Protocol Activity	Pre-treatment			Treatment Phase								Post-treatment
	Screening	Run-In		Day 1 (Randomization)	Day 4	Wk 2	Wk 4 (RC) ^a	Wk 6	Wk 10 (RC) ^a	Wk 11	Wk 12/ EOT ^b	
	Wk -3	Wk -2	Wk-1									
Hematology	X			X							X	
Calcitonin	X			X							X	
Serum β -hydroxybutyrate				X		X		X			X	
Urine dipstick/urinalysis				X							X	
Serum pregnancy test ⁿ	X										X	
Urine pregnancy test				X ^o								
Follicle-stimulating hormone ^p	X											
Trough Pharmacokinetic and Immunogenicity Anti-Drug Antibodies samples ^q				X		X		X			X	X
Non-trough Pharmacokinetic sample					X							
Fasting plasma, serum, and urine archive samples for exploratory research ^l				X							X	
Patient-Reported Outcomes ^r												
IWQOL-Lite		X									X	
Dispense diary containing Eating-related Concepts Questionnaire (ERCQ)		X						X				
Contact subjects to remind completion of the 7-day ERCQ diary									X			

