Completion of 7-day ERCQ diary				X-----X ^s							X-----X ^s	
PROMIS Physical Function Short Form (PROMIS SF 10a)		X		X							X	
Patient Global Impression Status (PGIS)		X ^t									X ^t	
Patient Global Impression of Change (PGIC)											X ^t	
Subject Counseling and Ongoing Review/Assessments												
Diet/exercise and hydration counseling and reinforcement ^u				X		X		X				
SMBG and hypoglycemia counseling ^{v,w}		X										
Dispense glucose meter, test strips, and blood sugar diary ^w		X		X		X		X				
Record SMBG level, hypoglycemic episodes, and concomitant medications ^{x,e}		X	X	X	X	X	X	X	X	X	X	
Review/discuss blood sugar diary (which includes SMBG results, hypoglycemia events, and concomitant medications)		X		X		X		X			X	

Protocol Activity	Pre-treatment			Treatment Phase								Post-treatment
	Screening	Run-In		Day 1 (Randomization)	Day 4	Wk 2	Wk 4 (RC) ^a	Wk 6	Wk 10 (RC) ^a	Wk 11	Wk 12/ EOT ^b	
Adverse Event reporting and review ^y		X		X	X	X	X	X	X	X	X	X

AE=adverse event; AHA=antihyperglycemic agent; BP=blood pressure; ECG=Electrocardiogram; eCRF=electronic case report form; EOT=end-of-treatment; ERCQ=Eating-related Concepts Questionnaire; FPG=Fasting plasma glucose; FSH=Follicle-stimulating hormone; HbA_{1c}= Hemoglobin A_{1c}; HR=heart rate; IWQOL-Lite=Impact Of Weight On Quality Of Life-Lite; IWRS=interactive web response system; PK=Pharmacokinetics; PROMIS SF 10a=Patient-Reported Outcomes Measurement Information System Physical Function Short Form 10a; RC=remote contact; SAE=serious adverse event; SMBG=Self-monitored blood glucose; Wk=Week.

- a) Study-site staff will contact subjects preferably by telephone to reinforce the adherence to diet and exercise, proper hydration, study drug dosing reminder, assessment of subjects' status, and compliance with the protocol procedures (eg, diary completion reminder).

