Counseling should be done by dietitians/nutritionists on Day 1 to provide assessment and recommendation on a reduced-calorie diet and exercise regimen ([Appendix 7](#), Standardized Nonpharmacologic Weight Reduction Therapy). In addition, subjects will be counseled on maintaining proper hydration throughout the study especially in circumstances of potential dehydration (eg, nausea and vomiting). At subsequent visits (Week 2 and Week 6), counseling and reinforcement of the recommended diet/exercise and hydration regimens will be conducted by a trained counselor. In addition, beginning at Week -2 visit, subjects will be counseled to comply and perform fasting SMBG testing at least 2 times per week. At each treatment visit, the investigator or qualified, assigned designee will review the subject's diaries, concomitant medications and the AEs that started or changed since the last visit.

The efficacy evaluation will include the percentage change in body weight from baseline as the primary efficacy endpoint.

Safety evaluations will include the monitoring of AEs (including protocol-specified AEs of interest), vital sign measurements, clinical laboratory tests (including serum chemistry, calcitonin, lipase, amylase, hematology, and urinalysis), physical examination including complete skin examination, serum/urine pregnancy testing, ECG, SMBG, assessment of hypoglycemia episodes, and review of concomitant medications. Refer to [Section 8.2](#), Safety Assessments, for further details.

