5.1. Inclusion Criteria

Each potential subject must satisfy all of the following criteria to be enrolled in the study:

1. Male or female (according to their reproductive organs and functions assigned by chromosomal complement)
2. 18 (or the legal age of consent in the jurisdiction in which the study is taking place) to 70 years of age, inclusive
3. BMI ≥ 35 to ≤ 50 kg/m² at screening
4. Stable weight (ie, change of $\leq 5\%$ within 12 weeks before screening based on medical or subject reported history)
5. HbA_{1c} of $\geq 6.5\%$ and $\leq 9.5\%$ at screening as determined by the central laboratory and meets one of the inclusion criteria below:
 - On diet and exercise alone ≥ 12 weeks prior to screening
 - On stable dose of single oral AHA or dual-combination oral AHAs for ≥ 12 weeks prior to screening (AHAs allowed at screening include: metformin, sulphonylureas, DPP-4 inhibitors, SGLT-2 inhibitors, and TZDs)

6. Subjects are, in the investigator's opinion, well-motivated, capable, and willing to:
 - perform fasting SMBG testing at least 2 times per week
 - learn how to self-inject treatment, as required for this study
7. On Day 1, subjects must have 100% compliance with the open-label placebo run-in medication based on unused prefilled safety injector(s), used empty study drug carton(s), and/or injections recorded in study drug diary during the pretreatment phase.
8. Willing and able to adhere to the prohibitions and restrictions specified in this protocol
9. Must sign an informed consent form (ICF) indicating that he or she understands the purpose of, and procedures required for, the study and is willing to participate in the study.
10. Women must be either:
 - postmenopausal, defined as:
 - >45 years of age with amenorrhea for at least 18 months, or
 - >45 years of age with amenorrhea for at least 6 months and <18 months and a serum follicle-stimulating hormone (FSH) level >40 mIU/mL (>40 IU/L), or
 - permanently sterilized (eg, bilateral tubal occlusion [which includes tubal ligation procedures as consistent with local regulations], hysterectomy, bilateral salpingectomy, bilateral oophorectomy); or otherwise be incapable of pregnancy, or

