8.2. Safety Assessments

Safety evaluations will include the monitoring of AEs (including protocol-specified AEs of interest), vital sign measurements, clinical laboratory tests (including serum chemistry, calcitonin, lipase, amylase, hematology, and urinalysis), physical examination including complete skin examination, serum/urine pregnancy testing, ECG, SMBG, assessment of hypoglycemia episodes, and review of concomitant medications.

At Week -2, subjects will be provided with and instructed on the use of a home blood glucose meter that will measure their fasting SMBG (to be done at least twice weekly). Subjects will be counseled on the signs/symptoms and how to manage an episode of hypoglycemia (see

[Appendix 8](#), Hypoglycemia: Definitions, Symptoms, and Treatment). In addition, subjects should be counseled to contact the site if their fasting SMBG consistently (ie, ≥ 3 days within a week) exceeds 200 mg/dL, and an FPG measurement to determine eligibility for glycemic rescue therapy should be obtained (see [Section 6.6](#), Glycemic Rescue Medication).

Investigators will remind subjects to contact the investigational sites in the presence of signs/symptoms that may be consistent with acute pancreatitis (see [Appendix 11](#), Pancreatitis Monitoring and Withdrawal Criteria), or in the presence of severe nausea/vomiting that limits the ability of the subject to keep adequate fluid intake even for a few hours, hence increasing the risk of dehydration and electrolyte imbalances, as well as DKA. Based on the assessment, the investigators should use their clinical judgment to determine whether the subject may require immediate medical attention (eg, emergency room visit) or whether the subjects should be scheduled as soon as possible for an unscheduled visit to undergo clinical and pertinent laboratory assessments, and if deemed appropriate by the investigator, study drug should be interrupted until results have been reviewed.

If a subject experiences an adverse event of vomiting assessed by the investigator as “severe” in intensity (see [Appendix 1](#), Adverse Events: Definitions and Procedures for Recording, Evaluating, Follow-up, and Reporting) lasting more than 24 hours and considered to be at least possibly related to study drug, the subject must be discontinued from study treatment (see [Section 7.1](#), Discontinuation from Study Drug).

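### The SMBG contact trigger needs three high days in a week, but subjects need only test twice a week, so a minimum tester on fixed days or calendar weeks can never meet it

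*Protocol*

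**What the plan says.** **Trigger.** Protocol 6.6 has subjects contact the site when fasting SMBG is consistently high, glossed as at least "3 days within a week) exceeds 200 mg/dL, and an FPG measurement to determine eligibility for glycemic rescue therapy should be obtained". The synopsis (Glycemic Rescue Medication) and 8.2 give the same rule. Whether a week means a calendar week or any 7 consecutive days is not stated.

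**Testing frequency.** Protocol 4.1: "subjects will be counseled to comply and perform fasting SMBG testing at least 2 times per week". The synopsis and inclusion criterion 6 (5.1) set the same minimum. Section 8.2 states the minimum and the trigger in one paragraph. No text in the two documents adds tests after a high reading.

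**Other routes to detection.**
- The Schedule of Activities (1.3) sets post-baseline FPG at Weeks 2, 6 and 12.
- The row beginning "Review/discuss blood sugar diary (which includes SMBG results, hypoglycemia events, and concomitant medications" is marked at clinic visits only.
- A separate row, for recording SMBG level, hypoglycemic episodes and concomitant medications, is marked from Week -2 to Week 12, including Weeks 4, 10 and 11.
- Footnote a lists what the remote contacts cover. It includes a general check of the subject's status but does not name SMBG values.
- Section 8 allows unscheduled samples for safety, and 8.2.4 provides central laboratory alerts without giving cut-offs.

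**Rescue.** Table 3 (6.6) bases rescue on FPG, not SMBG: above 270 mg/dL through Week 6 and above 240 mg/dL after that.

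**The concern.** A subject who does exactly what is asked, and no more, can have two readings above 200 mg/dL out of two, week after week, and never reach the point at which the protocol says to call. The rule should work for that subject.

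The rule carries weight in this trial. Protocol 2.3 accepts that glucagon agonism may raise plasma glucose in some subjects. It names the contact instruction as a response, with clinic FPG in addition. Section 4.2.1 cites regular fingerstick monitoring as a protection for all subjects. Exclusion criterion 4 (5.2) excludes only a Day 1 fasting fingerstick of 270 mg/dL or more, so a subject can start with readings already above 200 mg/dL. In the ongoing Phase 1 study (2.2), mean FPG rose by about 19 mg/dL at 10 mg, the top dose here, and fell by about 33 mg/dL on placebo. Those results are preliminary and come from groups of 8 active and 2 placebo subjects.

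The stretch most exposed is Week 6 to Week 12. The tighter 240 mg/dL cut-off applies there, but the only scheduled FPG in that period is at Week 12, when treatment ends.

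**Working it through.** The plan gives no figure to reproduce. The check compares two counts.

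**Inputs.** Trigger: at least 3 days above 200 mg/dL within a week (6.6, 8.2, synopsis). Tests: at least 2 a week (4.1, 5.1, 8.2, synopsis). Scheduled FPG after baseline: Weeks 2, 6 and 12 (1.3).

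**1. Calendar weeks, minimum testing.** There are 2 tests per week. Since 2 < 3, the trigger cannot be met on any choice of days.

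**2. Fixed days, rolling week, minimum testing.** There are C(7,2) = 21 weekday pairs. Any 7 consecutive days contain each weekday once, so each window holds exactly 2 tests. Enumeration over 42 days confirms a maximum of 2 for all 21 pairs. The probability of meeting the trigger is 0, even if 100% of readings are high.

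**3. Shifting days, rolling week, minimum testing.** Over two weeks there are 21 × 21 = 441 patterns. Of these, 245 (56%) contain a 7-day window with 3 or 4 tests. Over six weeks, 60,984 of 21^6 = 85,766,121 patterns (0.07%) never put 3 tests in a window. The trigger is therefore nearly always reachable at some point in this case. Patterns are weighted equally, so these are not rates of real behaviour.

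**4. More than the minimum.** Three tests a week on fixed days put 3 in every 7-day window, so the trigger can be met, but only if all three are high.

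**5. Gap.** Week 6 to Week 12 is 6 × 7 = 42 days with no scheduled FPG in between. If the Week 10 call does review SMBG, the longest stretch without such contact is (10 − 6) × 7 = 28 days.

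**6. Effect of two repairs.** This illustration is for a fixed-day tester over 6 weeks (12 routine tests), with readings assumed independent and p the chance that a reading is high.
- *Two or more high days in any 7.* Consecutive tests are at most 6 days apart in all 21 schedules, so two consecutive high readings meet the trigger.
- *Three days kept, with daily tests for 7 days after any high reading.* Simulated with 40,000 runs, routine tests on days 1 and 4, each high reading restarting the 7 days, stopping at first contact.

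| p | Current rule | 2 days in 7 | 3 days + daily retest | Mean tests under retest (to contact or Day 42) |
|---|---|---|---|---|
| 0.05 | 0 | 0.026 | 0.019 | 15.0 |
| 0.20 | 0 | 0.322 | 0.58 | 16.6 |
| 0.50 | 0 | 0.908 | 0.999 | not compared |
| 1.00 | 0 | 1 | 1 | 3 |

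The middle columns give the chance of at least one contact. Real fasting readings are likely correlated from day to day, so the table compares the rules and does not forecast contact rates.

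**The case against.** The strongest reply is that failure needs a particular subject. Two tests is a floor, and meters and strips are dispensed repeatedly and topped up as needed, so testing more often is supported. With a rolling week and varying days, the rule nearly always becomes reachable. The trigger is also only an early prompt, set well below the FPG rescue cut-offs, and nothing says it is the sole reason to call. Clinic FPG and diary review at Weeks 2, 6 and 12, laboratory alerts and unscheduled samples all remain. The blood sugar diary may already tell subjects to retest. All of this stands, and it limits the weight of the point. It does not make the written rule work for the minimum tester. Alerts need a sample, and an unscheduled sample needs someone to know that glucose is high.

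A second reply is that the SMBG-recording row is marked at Weeks 4 and 10, so the calls may already collect values. That is possible, and a reader should not infer that the documents leave SMBG out of those weeks altogether. But the row is also marked at Weeks -1 and 11, where no visit or call is listed, so it may mean recording by the subject. Footnote a does not settle it.

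A reader might also infer that the trigger can never fire for any compliant subject, or that hyperglycemia would go undetected. Steps 3 and 4 and the other safeguards contradict both. Nor do the documents support a claim of bias in the primary result. Protocol 9.4.1 excludes post-rescue weights, but SAP 5 and 5.2.3 drop that exclusion, and the SAP amendment history says non-glycemic endpoints are analysed regardless of rescue.

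**Conclusion.** The mismatch is real and conditional. For a subject who tests exactly twice a week, on fixed days or with weeks counted by calendar, the contact trigger is unreachable whatever the readings. Outside those conditions it can be met. This rests on the two rules as written and on the absence of any retest instruction in the protocol or SAP; a retest instruction in the diary would close the gap in practice, though the protocol should then state it. How many subjects test only at the floor cannot be estimated from the documents. The consequence is weaker subject-driven detection of hyperglycemia between visits, mainly in the nominal 42 days from Week 6 to Week 12. Severity is minor to moderate: the rule fails for some fully compliant subjects, but other safeguards partly cover them.

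**What to change.** Amend the synopsis, 6.6, 8.2 and the blood sugar diary instructions in one of two ways.

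1. **Preferred.** Keep 3 days, define a week as any 7 consecutive days, and require daily fasting tests for 7 days after any reading above 200 mg/dL. This keeps the sponsor's meaning of consistently elevated.
2. **Alternative.** Restate the trigger as fasting SMBG above 200 mg/dL on 2 or more days within any 7 consecutive days. This needs no extra testing.

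In either case, state in footnote a of the Schedule of Activities that the Week 4 and Week 10 calls review fasting SMBG values since the last visit and prompt an FPG if the trigger is met.

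The cost is a sentence in three protocol places, a diary line and one question in two existing calls. No visit is added and Table 3 does not change. The downside is some unscheduled FPG draws and, under the preferred option, extra fingersticks: in the illustration, about 15 to 17 tests over six weeks when 5% to 20% of readings are high, against 12 at the minimum.
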